2.4.1 Documenting Investigator-Confirmed Attacks

Accurate and complete documenting Investigator-confirmed HAE attacks is important for the study, as it will be used for the study primary endpoint analysis. All HAE attack information should be substantiated by supporting documentation and medical records.

The site should record the following information on each attack in the CRF:

- Start date and time of an attack.
- End date and time of an attack.
- Location(s) of HAE symptoms.
- HAE symptom description.
- HAE attack severity evaluation (refer to Section 2.4.1.3).

- Use of on-demand treatment (If yes, enter the following information in HAE treatment form):
 - Name of on-demand medication.
 - Dose(s) of on-demand medication(s) used.
 - Route(s) of administration of on-demand medication(s) used.
 - Start date and time of administration(s) of on-demand medication(s) used.
 - Select the identification number of the HAE attack the on-demand treatment was given for (to be selected from a list) in the CRF.
 - Administration of on-demand medication(s) at a study site, home, emergency room.

2.4.1.1 Attack Duration

The duration of an HAE attack will be reported by the investigator / delegate considering all available medical information including the onset of first symptom and resolution of last of symptom of each attack entered in the eDiary. Unless there has been a completely symptom-free 24-hour minimum separation between the onset and resolution of all symptoms, a single HAE attack will be documented on the basis of the earliest start and the latest end date of symptoms in the anatomic locations listed.

2.4.1.2 Attack Location

Hereditary angioedema attacks can occur in any anatomical location or multiple locations of the body and these locations are highly variable. An HAE attack may manifest itself in multiple anatomic locations. For example, swelling of the hand and abdomen may occur as symptoms of a single attack if they are temporally associated (ie, occurring at the same time or occurring within overlapping periods within 24 hours). Unless there has been a completely symptom-free 24-hour minimum separation between the onset of new symptom and resolution of prior symptoms in any / all location(s), a single HAE attack will be documented with all relevant locations listed in the CRF.

2.4.1.3 Attack Severity

The severity of each HAE attack (ie, mild, moderate, or severe) will be assessed by the investigator or designee based on the subject's description of the attack. The severity over the

time that the attack develops, progresses, and resolves can range from mild to severe. The overall attack severity will reflect the maximum intensity of the attack, as assessed by the investigator.

All attacks regardless of the severity should be associated with perceivable swelling and / or discomfort. Further qualifiers for attack severity are described below. Note that these may vary between subjects and attacks.

- **Mild**

- The HAE attack has little to no effect on daily activities.
- The use of HAE on-demand medication to treat the attack may not be necessary.
- Other concomitant medication (eg, analgesics) may be used to treat attack symptoms.

- **Moderate**

- The HAE attack causes daily activities to be difficult.
- Some assistance may be needed to complete daily activities.
- The use of HAE on-demand medication to treat the attack is probable.

- **Severe**

- The HAE attack causes marked limitation of daily activities.
- Medical assistance and intervention may be required, including at clinic emergency room visit or hospitalization.
- HAE on-demand medication is used to treat the attack.

2.0	02 Oct 2025	[name]	
• Updates due to Protocol Amendment 1 to consider transition to autoinjector device and dose modifications no longer being permitted.• Inclusion of additional subgroups and analysis windows.• Correction of the description of the Treatment Satisfaction for Medication Questionnaire version II derivations.• Consolidation of all information regarding adverse events in Section 11.• Formatting and abbreviation edits.• New analysis for number and proportion of attack-free days.• Removal of most Corona Virus Disease 2019 related analysis.• Removal of Mixed Model and Sidak correction of confidence intervals for analysis of quality of life endpoints.

2 List of Abbreviations

Abbreviation	Definition
ADaM	Analysis Data Model
AE	Adverse Event
AE-QoL	Angioedema Quality of Life Questionnaire
AESI	AE of Special Interest
AI	Autoinjector
ATC	Anatomical Therapeutic Chemical
ATS	All Treated Subjects
AUC	Area under the Curve
AUC _{0-30days}	Area under the Concentration-time curve from 0-30 days
BMI	Body Mass Index
CDISC	Clinical Data Interchange Standards Consortium
CI	Confidence Interval
C _{max}	Maximum Concentration
COVID-19	Corona Virus Disease 2019
CSR	Clinical Study Report
DBL	Database Lock
eCOA	electronic Clinical Outcome Assessment
eCRF	Electronic Case Report Form
EOS	End of Study
EOT	End of Treatment
FXII(a)	(Activated) Factor XII
HAE	Hereditary Angioedema
ICH	International Conference on Harmonisation
ID	Identifier
IDMC	Independent Data Monitoring Committee
IGART	Investigator's Global Assessment of Response to Therapy
ISR	Injection site reaction
IRT	Interactive Response Technology
MCID	Minimal Clinically Important Difference
MedDRA	Medical Dictionary for Regulatory Activities
nC1-INH	Normal C1-esterase inhibitor
NSD	Needle safety device
PARM	Planned Analysis Review Meeting
PD	Pharmacodynamics

Abbreviation	Definition
PK	Pharmacokinetics
PP	Per Protocol
PT	Preferred Term
QoL	Quality of Life
SAE	Serious Adverse Events
SAP	Statistical Analysis Plan
SC	Subcutaneously
SD	Standard deviation
SDTM	Study Data Tabulation Model
SGART	Subject's Global Assessment of Response to Therapy
SMQ	Standardised MedDRA Query
SOC	System Organ Class
TEAE	Treatment Emergent Adverse Event
TFL	Tables, figures, listings
Tmax	Time to Maximum Concentration
TSQM II	Treatment Satisfaction for Medication Questionnaire version II
WHODrug Global	World Health Organization Drug Global
WPAI:GH	Work Productivity and Activity Impairment: General Health

Glossary of Terms

Include important definitions which are referred to multiple times in the SAP and providing definitions in the glossary facilitate understanding.

Term	Definition
CSL312-naïve subjects	Subjects who did not previously participate in CSL312_2001 or CSL312_3001.
C1-INH HAE	Hereditary angioedema type 1 (quantitative decrease in C1-esterase inhibitor plasma concentrations) and hereditary angioedema type 2 (dysfunctional C1-esterase inhibitor present in normal or high plasma concentrations).
nC1-INH	Hereditary angioedema with normal C1-INH, formerly known as type 3.
Treatment-naïve subjects	Subjects who did not receive any dose of CSL312 before this study. This includes CSL312-naïve subjects and subjects who received placebo in previous studies.

3 Purpose

This Statistical Analysis Plan (SAP) provides a detailed and complete description of the planned statistical analyses of the study CSL312_3002 [An Open-label Study to Evaluate the Long-term Safety and Efficacy of CSL312 (Garadacimab) in the Prophylactic Treatment of Hereditary Angioedema] to support the Clinical Study Report (CSR).

This SAP complies with the International Council for Harmonisation (ICH) E9 ‘Statistical Principles for Clinical Trials’ and E9(R1) ‘Statistical Principles for Clinical Trials: Addendum on Estimands and Sensitivity Analysis in Clinical Trials’, and is based upon the following study documents:

- Clinical Study Protocol, Amendment 1, dated 27 Oct 2022.
- electronic Case Report Form (eCRF), V6.0, dated 18 Feb 2025.

All decisions regarding the final analysis of the study results, as defined in this SAP, have been made before database lock (DBL) of the study data.

Deviations from the analyses in this SAP will be detailed in the CSR.

4 Study Design

This is a multicenter, open-label, phase 3b study designed to investigate long-term safety and efficacy of CSL312 when administered once monthly for at least 12 months. Subjects eligible to participate in this study may be:

[figure not shown]
- Subjects who participated in the phase 3 double-blind study CSL312_3001,
- Subjects who participated in study CSL312_2001,
- CSL312-naïve subjects with C1-INH HAE Type 1 / 2.

The study consists of 4 periods: Screening, Run-in (only for CSL312-naïve subjects), Open label Treatment Period, and a Follow-up Period.

For subjects naïve to CSL312, there will be a Screening Period of up to 1 month followed by a Run-In Period, which may last at least 1 month and up to 2 months. CSL312-naïve subjects who meet all eligibility criteria during the Run-In Period will then enter the Treatment Period. Subjects who complete Studies CSL312_3001 and CSL312_2001 according to their respective protocols will be offered the opportunity to continue treatment by entering the CSL312_3002 Open-label Treatment Period. Subjects who reach the end of treatment or terminate the study early will have a follow-up phone call 2 months after the End of Treatment (EOT) Visit. Subjects may switch to a HAE prophylaxis medication during the Follow-up Period.

The study schematic is shown in Figure 1.

Figure 1 CSL312_3002 Study Schematic

EoT = end of treatment; HAE = hereditary angioedema; OL = open-label

^a Follow-up Visit may be conducted via telephone instead of at the study site. This visit is only applicable for subjects ending study participation following the original protocol (for subjects who consent into the Protocol Amendment 1, refer to Schedule of Assessments: Treatment Period for All Subjects Under Amendment 1).

4.1 Objectives and Endpoints

The primary objective of the study is to evaluate the long-term safety of subcutaneous (SC) administration of CSL312 in the prophylactic treatment of subjects with C1-INH HAE.

Table 1 Primary Objective and Endpoint

Objectives	Endpoints	Summary Measure(s)
Primary	Treatment-emergent Adverse Events (TEAEs)	Number of subjects, percentage of subjects, and number of events as well as the event rates per injection and per subject year.

The secondary objectives of this study are to evaluate:

1. Long-term efficacy, including patient-reported assessment of response to therapy,
2. Long-term safety.

Table 2 Secondary Objectives and Endpoints

Objectives	Endpoints	Summary Measure(s)
1.	Time-normalized number of HAE attacks	The time-normalized number (per month and year) of HAE attacks for the run-in and Treatment period.
1.	The reduction in the attack rate during the Treatment Period compared to the Run-in Period	The percentage reduction and the number of subjects experiencing at least $\geq 50\%$, $\geq 70\%$, $\geq 90\%$ or equal to 100% (attack free) reduction in the time-normalized number of HAE attacks on Treatment compared to Run-in Period.
1.	The time-normalized number of HAE attacks requiring on-demand treatment	The time-normalized number (per month and year) of HAE attacks requiring on-demand treatment in subjects on treatment.
1.	The time-normalized number of moderate and / or severe HAE attacks	The time-normalized number (per month and year) of moderate and / or severe HAE attacks in subjects on treatment.
1.	Subject's Global Assessment of Response to Therapy (SGART)	Number and percentage of subjects rating their response to therapy as good or excellent.

Objectives	Endpoints	Summary Measure(s)
2.	
 • Serious Adverse Events (SAEs) • Deaths • Related TEAEs • TEAEs leading to study discontinuation • TEAEs by severity • Anti-CSL312 antibodies • Laboratory findings reported as an adverse event (AE) • Adverse Events of Special Interest (AESIs), ie, thromboembolic events, abnormal bleeding events, severe hypersensitivity, including anaphylaxis events • TEAE (for nC1-INH subjects only) 	The number and percentage of subjects experiencing the specified safety events on treatment with CSL312.

The exploratory objectives of the study are to evaluate the efficacy and quality of life (QoL) associated with the use of CSL312 in subjects with HAE. Pharmacokinetics (PK) and pharmacodynamics (PD) will also be evaluated.

The exploratory efficacy endpoints are the time to first attack after Day 1 administration and after Day 14 for CSL312-naïve subjects, and the maximum attack-free time for all subjects.

Exploratory QoL endpoints include the following:

- Subject reported outcome measures: Angioedema Quality of Life Questionnaire (AE-QoL), Work Productivity and Activity Impairment: General Health (WPAI:GH) and Treatment Satisfaction for Medication Questionnaire version II (TSQM II),
- Investigator's Global Assessment of Response to Therapy (IGART).

The exploratory PK and PD endpoints are:

- CSL312 concentrations at scheduled time points,
- Activated Factor XII (FXIIa)-mediated kallikrein activity at scheduled time points,

- CSL312 PK parameters (maximum concentration [C_{max}], time to maximum concentration [T_{max}], area under the concentration-time curve from 0-30 days [$AUC_{0-30days}$]).

4.1.1 Primary Study Hypotheses

There are no formal hypotheses for this study. Instead, this study is designed for the assessment of long-term safety and efficacy of CSL312 (200 mg) in HAE subjects.

4.2 Study Treatments

There will only be a single treatment arm in this study with the study treatment being CSL312.

All subjects who meet the criteria to enter the study will be assigned to 1 dose of CSL312, 200 mg, to be given SC once monthly for a minimum of 12 doses. For CSL312-naïve subjects, a loading dose of 400 mg (two 200 mg doses) will be administered SC on the first month, then 200 mg once per month in subsequent months. Per original protocol, the dose could have been increased in 200 mg increments for safety reasons and the maximum allowed dose for C1-INH subject was 400 mg per month. The maximum allowed dose for nC1-INH subjects was 600 mg per month. Per Amendment 1, no dosing modifications will be permitted.

No dosing modifications occurred prior to Amendment 1.

All subjects will be trained in CSL312 self-administration at Baseline (Day 1 of the Treatment Period). Subjects who participated in Study CSL312_3001 and subjects naïve to CSL312 will also be trained in CSL312 self-administration at the Month 1, 2, and 3 visits. Starting at Month 4, these subjects will self-administer monthly at home. Subjects who participated in Study CSL312_2001 will have the first dose administered at the site and will self-administer CSL312 at home thereafter. Subjects will complete a medication dosing electronic diary (eDiary) for all doses administered, including doses administered at the site.

Per Amendment 1, subjects or caregivers will SC administer CSL312 200 mg autoinjector (AI) instead of CSL312 200 mg needle safety device (NSD). The first administration with CSL312 200 mg AI will be on site, and training will be provided for subjects and caregivers. Additional CSL312 200 mg AI administration training at subsequent scheduled onsite visits may be provided if it is requested. Subsequent administrations with CSL312 200 mg AI will occur at home (either self-administered or with the help of a caregiver).

The dose and dosing regimen will continue to be 200 mg once monthly. Subjects who decline switching to CSL312 200 mg AI and who have participated in the study for at least

12 months will receive 1 more dose of CSL312 200 mg NSD at the time of the scheduled site visit and subsequently proceed with the EOT Visit 1 month later, as well as a Follow-up Visit 2 months after the EOT Visit, as per the original protocol.

4.3 Randomization Procedures and Blinding

Not applicable, this is an open-label study with a single treatment arm.

4.4 Determination of the Sample Size

Approximately 150 subjects (including 8 Japanese subjects) are planned to be enrolled into the study and a minimum of 100 subjects are planned to receive treatment for a minimum of 12 months.

This is a single arm study without a control arm. The sample size for this single arm, open-label study is not based on a formal statistical sample size calculation but on the guideline E1A issued by the International Conference on Harmonisation, March 1995. The sample size of 100 subjects allows observation of ≥ 1 AE with a probability of 3% at 95% confidence.

4.5 Planned Interim Analyses

Two interim analyses are planned for this study.

4.5.1 Interim Analyses Other Than Sample Size Re-estimation

Interim analyses will be conducted in order to support regulatory activities. The results of the interim analyses are not intended to be used to stop, adapt the study, or adjust the sample size.

As this study is an open-label, single arm study no blinding needs to be protected. The same CSL and Parexel staff who will be involved in the final analysis, will also execute the interim analyses.

The sample size is not based on a formal statistical sample size calculation but on the guideline E1A and therefore no overall Type I or II error rates need to be controlled.

An interim analysis is planned to be conducted when approximately 100 subjects have 12 months exposure of CSL312 in Study CSL312_3002 alone or across all studies, ie, CSL312_2001, CSL312_3001 and CSL312_3002, dependent on subjects' enrollment in Study CSL312_3002.

The analyses performed and the table, listing, figure outputs generated for the interim analyses will follow the final SAP and consider all data up to the defined data cut-off.

In addition, further interim analyses will be conducted on an as-needed basis in order to support regulatory activities.

4.5.2 Independent Data Monitoring Committee

An independent data monitoring committee (IDMC) will be established to monitor the efficacy and safety data generated during the study.

The IDMC will review accumulating data from the ongoing study. Based on these reviews, the IDMC will advise on the further conduct of the study. No success or futility thresholds will be set for the IDMC reviews. CSL will continue the study unless a safety issue is confirmed that warrants study termination. The composition, activities, analyses, responsibilities, and timing of meetings of the IDMC will be described in the IDMC charter.

5 Changes from the Protocol Planned Analyses

This version of the SAP includes several changes that reflect Amendment 1 of the Clinical Study Protocol. This section only describes changes to the analyses that were not already described in the protocol amendment.

The scope of analysis related to the Corona Virus Disease 2019 (COVID-19) pandemic has been reduced to items directly related to the primary endpoint.

6 Study Analysis Sets

6.1 Screened Analysis Set

The Screened Analysis Set comprises all subjects who provide written informed consent.

6.2 All Treated Subjects Analysis Set

The All Treated Subjects (ATS) Analysis Set comprises all subjects in the Screened Analysis Set who were assigned to treatment. The ATS Analysis Set will be analyzed using the treatment to which the subject was assigned, regardless of the treatment actually received.

Technical Note: inclusion in the ATS will be determined based on whether the subject is marked as eligible on the Subject Eligibility form.

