Safety will be assessed by all AEs, TEAEs, vital signs, physical examinations, hematology, biochemistry, urinalysis, coagulation parameters, and anti-drug antibodies.

Pharmacokinetics	Plasma samples will be collected for assessment of CSL312 concentrations. From a PK subgroup analysis in CSL312-naïve adult subjects, CSL312 PK parameters (maximum concentration [C_{max}], time to maximum concentration [T_{max}], area under the concentration-time curve from 0-30 days [$AUC_{0-30days}$]) will be derived.
-------------------------	---

Pharmacodynamics	Plasma samples will be collected for assessment of FXIIa-mediated kallikrein activity.
-------------------------	--

Other Assessments	Other assessments to evaluate quality of life and response to treatment will be obtained using the Angioedema Quality of Life (AE-QoL) questionnaire, the Work Productivity and Activity Impairment: General Health (WPAI:GH) questionnaire, the Treatment Satisfaction for Medication Questionnaire version II (TSQM II), and the Subject and Investigator Global Assessment of Response to Treatment (SGART and IGART).
--------------------------	---

Statistical Analyses

A minimum of 100 subjects are planned to receive treatment for a minimum of 12 months. This is a single arm study without a control arm. The sample size for this study is not based on a formal statistical sample size calculation but on the guideline E1A issued by the International Conference on Harmonisation, March 1995. The sample size of 100 subjects allows observation of ≥ 1 AE with a probability of 3% at 95% confidence.

The primary endpoint, TEAEs for all C1-INH HAE subjects receiving CSL312 once monthly, independent of the use of CSL312 200 mg AI or CSL312 200 mg NSD, will be summarized using the Safety Analysis Set, defined as all subjects who receive at least 1 dose of CSL312. The TEAEs will be assessed overall and by the use of CSL312 200 mg AI or CSL312 200 mg NSD. TEAEs are AEs that start on or after the date and time of the first administration of study treatment until the Follow-up Visit. TEAEs with completely or partially missing date or time will be considered treatment-emergent following the worst-case principle, unless the partial date clearly indicates that the AE started before the first administration of study treatment.

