10.2.2 All Treated Subjects Analysis Set

The All Treated Subjects (ATS) analysis set comprises all subjects in the Screened analysis set who were assigned to treatment. The ATS analysis set will be analyzed using the treatment to which the subject was assigned, regardless of the treatment actually received.

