6.3 Safety Analysis Set

The Safety Analysis Set comprises all subjects in the ATS Analysis Set who receive at least 1 dose of investigational product (IP) and will be analyzed using the actual treatment received. The actual treatment is planned to be CSL312 for all subjects.

Technical Note: The handling of unplanned dosing deviations for individual subjects will be discussed and decided at the Planned Analyses Review Meeting (PARM). Unless stated otherwise below, the treatment will be considered the same whether administered with NSD or AI.

The loading dose for CSL312-naïve subjects will be shown as part of the 200 mg dose.

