9.2 Protocol Deviations

All identified protocol deviations throughout the study will be listed prior to DBL and will be classified into minor/major by CSL. Major protocol deviations are defined as deviations that could have a significant effect on the subject's safety, rights, or welfare and/or on the integrity of the study data.

The protocol deviations' classification into minor and major will be reassessed under statistical considerations. During the PARM, the classification and the subject's assignment to

the analysis sets will be discussed in detail. The Planned Analysis Review report will include these decisions and classifications and will be approved before each data-cut for interim analyses and prior to DBL for final analysis.

Possible major protocol deviations especially include the following but are not limited to:

Potential Major Protocol Deviations	Potential Exclusion From Analysis Set
Subject did not provide informed consent (informed consent date missing)	Screening, Safety, ATS, PP, PK, PD
Subject assigned to treatment but not treated with study treatment	Safety, PP, PK, PD
Subject assigned to treatment and treated but does not have at least one measurable PK concentration	PK
Subject assigned to treatment and treated but does not have at least one PD measurement	PD
Subject assigned to treatment and treated but violated inclusion or exclusion criteria	PP, potentially others to be discussed during the PARM
Subject assigned to treatment and treated but treatment compliance outside 80-120%	PP, potentially also PK, PD
Subject assigned to treatment and treated but received prohibited concomitant medication	PP, potentially also PK, PD

Presumably other protocol deviations will be classified as major and lead to the exclusion of subjects or data from analysis sets.

Prior to the PARM, a list of concomitant medications used in the study will be provided to CSL as an Excel file in the same format as the corresponding listing of concomitant medications in the table, figure, and listing (TFL) shells. This Excel file will be reviewed by CSL and concomitant medication potentially interfering with the PK/PD analysis or with the efficacy analysis will be flagged. Subjects with such a concomitant medication flagged may be excluded from the respective analysis set.

The following listings will be provided using the Screened Analysis Set:

- Planned and actual treatment.

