10.6 Treatment Compliance

Information about administered doses is taken from the subject diary. Details about any issues with the dosing device (incomplete dose, device malfunction, use error) are recorded on the Device Event page of the eCRF.

The calculation of compliance will be based on the number of injections taken as planned and the number of planned injections:

$$\text{Compliance}[\%] = 100 \times \frac{\text{Actual Number of Injections Taken as Planned}}{\text{Planned Number of Injections}}$$

The number of planned doses is calculated and rounded down to the next integer as:

$$\text{Planned Number of Injections} = \text{floor}\left(\frac{\text{Duration of the treatment period [days]}}{30}\right)$$

As this calculation considers that the last dose should be taken 30 days prior to the EOT Visit, for interim analysis the following rule will be used instead for subjects still ongoing at the time of the data-cut:

$$\text{Planned Number of Injections} = 1 + \text{floor}\left(\frac{\text{Duration of the treatment period [days]}}{30}\right)$$

An injection counts as “taken as planned” if a dose is recorded in the eDiary and the “Incomplete Dose” field is not checked on the corresponding Device Event page. If necessary, dose diary data will be matched to data from the Device Event page by date and subject number.

For calculating treatment compliance, the loading dose is counted as a single injection.

The following summary will be provided using the ATS Analysis Set:

- Number of SC injections received,
- Overall compliance (%),
- Number and percentage of subjects with overall compliance categorized by < 80%, 80%-100% and >100%,
- Number of injections with not the full volume administered,
- Number of use errors,
- Number of device malfunctions by category of malfunction,
- Number of other issues.

Compliance data will be listed together with exposure date, see Section 11.1.

11 Safety Analyses

All safety analyses will be based on the Safety Analysis Set as defined in [Section 6.3](#).

In general, all tables stated to be provided for subgroups are conditional on there being at least 5 subjects in that subgroup who are included in the Safety Analysis Set.

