11.3 Analysis of Primary Safety Endpoint

All analyses described in this section are applicable for C1-INH HAE subjects only. TEAEs will be presented for the following:

- All subjects in the Safety Analysis Set (all subjects on 200 mg CSL312 once monthly, independent of the use of CSL312 200 mg AI or CSL312 200 mg NSD).
- Subjects on 200 mg CSL312 using AI.
- Subjects on 200 mg CSL312 using NSD.

TEAEs will be summarized by the number of subjects and percentage of subjects experiencing at least 1 TEAE, the number of events, as well as the event rates per injection and per subject year.

TEAE rates per injection will be calculated as follows:

$$\text{TEAE Rate per Injection} = \frac{\text{Number of TEAEs}}{\text{Number of injections}}$$

where the number of injections will be the sum of the injections that subjects received during the respective safety evaluation period with the respective device (NSD, AI, or overall) the TEAE is assigned to.

TEAE rates per subject years will be calculated as follows:

$$\text{TEAE Rate per Subject Year} = \frac{\text{Number of TEAEs}}{\text{Subject years}}$$

where subject years will be the sum of the time in years that subjects were exposed to study treatment using that device (NSD, AI, or overall) during the respective safety evaluation period.

An overview summary of TEAEs will be provided including:

- TEAE,
- SAEs,
- Deaths,
- ISRs,
- TEAEs occurring within 24 hours of start of IP administration,
- SAEs occurring within 24 hours of start of IP administration,
- Related TEAEs,
- Related SAEs,
- TEAEs leading to study discontinuation,
- TEAEs in each severity category,
- ISRs, in each severity category,
- TEAEs in each outcome category,
- SAEs in each severity category,
- SAEs in each outcome category,
- AESIs, both as reported by the investigators and as identified via SMQ (see [Section 11.4](#) for definitions).

A summary table by SOC and PT will be provided.

These two summaries will exclude all TEAEs clearly identified to be related to an HAE therapy other than CSL312 during the Follow-up Period. Both summaries will be repeated for TEAEs that can clearly be identified to be related to an HAE therapy medication other than CSL312.

To evaluate the COVID-19 impact on the primary endpoint the overview summary of TEAEs and the summary table by SOC and PT will be repeated as a sensitivity analysis excluding all COVID-19 related TEAEs (per the corresponding SMQ).

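### The SAP flags All Treated Subjects by an eligibility mark and takes the Safety set from it, so a subject dosed while marked ineligible would leave the primary safety analysis

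*SAP*

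**What the plan says.** **ATS.** Protocol 10.2.2 says that the set "comprises all subjects in the Screened analysis set who were assigned to treatment", and SAP 6.2 repeats that definition. The technical note in SAP 6.2 then gives the working rule: "inclusion in the ATS will be determined based on whether the subject is marked as eligible on the Subject Eligibility form". The note tests neither assignment nor dosing.

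**Safety.** The protocol describes this set in two ways. The synopsis has the "Safety Analysis Set, defined as all subjects who receive at least 1 dose of CSL312", with no further condition. Protocol 10.2.3 requires ATS membership as well as a dose, and SAP 6.3 follows it: "The Safety Analysis Set comprises all subjects in the ATS Analysis Set who receive at least 1 dose of investigational product (IP"). The Per-protocol (PP) set is also drawn from ATS (SAP 6.4), and the PK and PD sets are drawn from Safety (SAP 6.5 and 6.6).

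**Use.** SAP 11 opens with: "All safety analyses will be based on the Safety Analysis Set as defined in" SAP 6.3. SAP 11.3 applies that set to the primary TEAE summaries, restricted to C1-INH HAE subjects.

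**Deviations.** The table in SAP 9.2 has a row for "Subject assigned to treatment and treated but violated inclusion or exclusion criteria". It names PP as the potential exclusion and leaves other sets to the Planned Analysis Review Meeting (PARM). SAP 5, on changes from the protocol's analyses, does not mention the eligibility-form rule.

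**The concern.** A safety population should depend on exposure. Here it depends on a form entry about eligibility, one step removed. The eligibility mark and the assignment are separate pieces of data: the Day 1 schedule lists confirmation of eligibility and IRT kit assignment as separate procedures, so they can disagree. When they disagree for a dosed subject, the literal rule follows the form.

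The primary endpoint is TEAEs. A dosed subject who is left out takes events, injections and subject-years out of the primary tables together. For common events this hardly matters. For a serious event, an adverse event of special interest or a death, one subject may carry the only case in the study.

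**Working it through.** **1. Apply the definitions in sequence.** The inputs are SAP 6.2 (definition and technical note), SAP 6.3, protocol 10.2.2 and 10.2.3, and the synopsis.

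| Subject | ATS by the SAP note | Safety by SAP 6.3 with the note | Safety with ATS by assignment | Safety by synopsis |
|---|---|---|---|---|
| Assigned, dosed, marked eligible | in | in | in | in |
| Assigned, dosed, marked not eligible | out | out | in | in |
| Marked eligible, never assigned or dosed | in | out | out | out |

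Only the second row changes the Safety set. With ATS based on assignment, protocol 10.2.3 and the synopsis agree on all three rows. The form-based note is what separates them.

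**2. Check the plan's own figure.** SAP 4.4 and protocol 10.1 link 100 subjects with an event probability of 3% and 95% confidence.

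- All 100 analysed: 1 − 0.97^100 = 0.952, which reproduces the stated 95%.
- One lost: 1 − 0.97^99 = 0.951.
- Five lost: 1 − 0.97^95 = 0.945.

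The losses of one and five are assumed for illustration. The sample-size statement is essentially unaffected.

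**3. Effect on a rare event.** Assume that about 150 subjects are dosed (the planned enrolment) and that one of them is excluded by the rule.

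- Only case excluded: 1/150 = 0.67% becomes 0/149 = 0%.
- One of two cases excluded: 2/150 = 1.33% becomes 1/149 = 0.67%.

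**4. Effect on rates.** For TEAEs per injection and per subject-year, numerator and denominator fall together. The direction of any change cannot be known in advance.

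**The case against.** The strongest reply is that the note only puts assignment into practice. In a single-arm study, protocol 5.1.3 and 6.1 assign the 200 mg regimen to every subject who meets the entry criteria. Eligibility is confirmed before the Treatment Period, and CSL312-naïve subjects who do not qualify are Run-in failures. If sites follow the protocol, the mark and the assignment select the same people. This stands, and it is why cases should be rare. It does not settle the matter, because the definition matters only when something has gone wrong. The form itself is not in the documents, so whether its entry can be changed later cannot be seen.

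There are also partial safeguards. The PARM discusses set membership before each interim data cut and before database lock. SAP 9.1 lists reasons for exclusion from sets, and SAP 11.2 lists all adverse events whenever they occurred. A case could therefore be seen, but none of these rules returns the subject to the primary counts.

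A reader might infer more than the documents support:

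- **That the SAP introduced the nesting.** Protocol 10.2.3 already has it. The SAP added the form criterion.
- **That SAP 9.2 says the opposite of SAP 6.2.** It names PP and expressly leaves the other sets open.
- **That late entrants approved by the sponsor, or subjects with an overlooked criterion, would be lost.** Late entry with approval is a permitted route, and a site that misses a criterion would normally mark the subject eligible. Such subjects stay in Safety unless the form is later changed or the PARM removes them.
- **That marking undosed subjects eligible distorts the safety results.** A subject without a dose cannot enter Safety.

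**Conclusion.** The point holds as a defect in a written rule. As worded, the SAP removes from the primary safety analysis any subject dosed while the form records not eligible, and this conflicts with the synopsis. The number affected may be zero. The documents give no rate, so no expected count can be stated. Nor do they show that such subjects would be at higher risk than others. No planned figure changes materially. What is at stake is an individual rare event, as in 1/150 against 0/149, which assumes about 150 dosed subjects and one excluded case. The study is open-label with a single arm, so a PARM decision on such a case would be made with the subject's outcome known. A fixed rule is preferable to that. The change should be made before database lock, mainly because it costs so little.

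**What to change.** 1. **SAP 6.3:** define the Safety Analysis Set as everyone given one or more doses of CSL312, whatever the eligibility mark, in line with the synopsis.
2. **SAP 5:** record this as a clarification of protocol 10.2.3, which nests Safety in ATS.
3. **SAP 6.2, technical note:** derive ATS from actual assignment to treatment (IRT kit assignment for Treatment Day 1) in place of the eligibility mark.
4. **SAP 9.2:** leave the handling of eligibility violations for PP and the other sets as it is, and add that a dosed subject is not removed from Safety because of such a violation. The separate row on missing informed consent is not affected.

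The cost is a few sentences and changed derivations for the ATS and Safety flags. SAP 8.2.6 says that planned vial numbers from IRT and administered vial numbers are both collected, so no new data are needed. If no dosed subject was marked ineligible, no Safety result changes.
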